## **4. Investigation Design**

### **4.1. Study Summary**

This non-significant risk post-market clinical study utilizes a prospective design to compare patient Oral Health Related Quality of Life (OHRQoL) wearing the arylketone polymer (AKP) Removable Partial Denture (RPD) to their baseline Oral Health Related Quality of Life (OHRQoL) while wearing a Cobalt Chrome (CoCr) Removable Partial Denture (RPD). The study is intended to simulate actual fitting and use to allow the gathering and analysis of data on the comparative oral health related quality of life (OHRQoL) of the arylketone polymer (AKP) and cobalt chrome (CoCr) denture frames.

### **4.2. Number of Patients and Investigation Sites**

A minimum of 40 patients will be enrolled at a maximum of 3 sites in the United States and United Kingdom. It is expected that each site will enroll a minimum of 10 patients.

## 5. Investigational Device

The Ultaire™ arylketone polymer (AKP) prostheses are milled from the Dentivera™ Milling Discs using available dental Computer Aided Design / Computer Aided Manufacturing (CAD/CAM) systems. The Dentivera™ Milling Disc is a thermoplastic denture base resin designed for the manufacture of full and partial removable dentures and implant overdentures.

**Image 1: Ultaire™ AKP Removable Partial Denture in model**

**Image 2: Ultaire™ AKP Removable Partial Denture**

### 5.1. Manufacturer Information

The intended use of the arylketone polymer (AKP) denture frames are supported by the device master filing submitted to the FDA in July 2015. Solvay Dental 360™ received FDA clearance for this denture relining, repairing, and rebasing resin as defined under 21 CFR 872.3760, on June 15, 2016.

The Dentivera™ Milling Disc resin testing showed that the material is in accordance with the *ISO 20795-1: Dentistry - Base polymers Part 1: Denture base polymers* standard relating to mechanical properties of denture base materials.

Biocompatibility testing has been completed on the Dentivera™ Milling Disc resin in accordance with ISO 10993-1:2009 (Biological Evaluation of Medical Devices – Part 1: Evaluation and Testing within a risk management process). The following biocompatibility tests were performed: cytotoxicity, sensitisation, irritation, systemic toxicity, subchronic toxicity, implantation, genotoxicity, pyrogenicity, mutagenicity, and physical-chemical testing.

The device milling facility for this clinical trial is ISO 13485 certified, fully audited and qualified by the study Sponsor.

### 5.2. Packaging and Labelling

All denture frames utilised for this study will be labelled with a unique identifier (reference number). The reference number will be recorded in clinical records (source data) and Electronic Data Capture System (EDC)/Case Report Form (eCRF).

The arylketone polymer (AKP) denture frames will be shipped in commercially available packages. All study products must be kept in a secure place under appropriate storage conditions, away from sunlight, as per the instructions for use.

[figure not shown]

Figure 1: Dentivera Milling Disc Single Pack Shelf Box Label

### 5.3. Device Accountability

Each denture frame has a unique identifier (reference number) that will be recorded on the study device accountability log. All devices received and shipped must be recorded on this log and kept current in the Electronic Data Capture system (EDC/eCRF) and the Investigator Site File (ISF).

### 5.4. Device Training/Experience

The fitting and adjustments, completed by the dentist (investigator), of removable partial dentures (RPD) are standard of care.

The design of each arylketone polymer (AKP) denture frame will be agreed jointly by the clinician (the PI or delegated clinician at each site) and the milling facility prior to production. The approval will be recorded by the clinicians' signature on the Case Report Form (eCRF) prior to production.

## 6. Cohort Study Subject Selection

All subjects who fulfil the inclusion criteria will be invited to participate by signing a study informed consent. Subjects will only be considered enrolled once they sign the study consent form provided.

## 6.1. Inclusion Criteria

- Adults from age 18 upwards:
- With the absence of 4 or less teeth per saddle, excluding third molars
- Partial denture in one arch only
- With previous denture wearing experience, and Cobalt Chrome (CoCr) Removable Partial Denture (RPD) fitted in the previous 60 months and the patient is currently and routinely wearing the denture
- With a stable oral health in terms of absence of disease activity affecting the periodontium, dental hard tissues (caries), pulp and the structural/aesthetic integrity of restored teeth
- With at least 1 posterior natural tooth occlusal stop (molar or premolar)
- Class I, Class II and Class III (Kennedy's Classification)
- Occlusal spacing (static and dynamic) available around clasp assembly including the occlusal rest

## 6.2. Exclusion Criteria

- Patients requiring extensive treatment prior to the provision of a removable partial denture (RPD)
- Patients with active primary disease; caries, periodontal disease or symptoms of pulpal or apical pathology to the remaining teeth
- Patients with irreversibly compromised structural/aesthetic integrity of restored teeth that cannot be restored as part of the provision of treatment
- Patients with an opposing Removable Partial Denture (RPD). Removable Partial Denture (RPD) to only be in one arch and must oppose a full denture or a dentate arch which provides a stable occlusal relationship

## 6.3. Subject Withdrawal and Discontinuation

During the course of the study Subjects will be or may elect to withdraw from further treatment and assessments through any of the following reasons:

- Subject's rescission of consent
- Any unexpected adverse device effect which is, in the opinion of the Principal Investigator, related to the device and will endanger the wellbeing of the subject if treatment is continued
- The development of any undercurrent illness(es), infection or condition(s) that might interfere with the protocol
- Any problem deemed by the Principal Investigator and/or *Solvay Dental 360™* to be sufficient to cause discontinuation
- Subject Lost to Follow-Up

All subjects who discontinue due to an unexpected adverse device effect, directly related to the study, will be treated until the effect resolves. The Principal Investigator will clearly document the date and reason(s) for subject withdrawal in his/her Case Report Form (eCRF) and the monitor must be notified.

A subject will be classified as lost to follow up only if, he/she has failed to return to the required study visits and his/her dental status remains unknown, despite 3 documented attempts to contact the subject via telephone, fax, email, and/or certified letter.

## 6.4. Procedures for handling incorrect enrolled subjects

Subjects not meeting the inclusion/exclusion criteria for a study should not be enrolled into the study. If a subject is enrolled who does not meet inclusion/exclusion criteria, a protocol deviation will be completed and this will be noted in the final report.

## 7. Investigation Procedures

### 7.1. Screening Evaluations

#### 7.1.1. Informed Consent

After a normal clinical assessment, the Principal Investigator (PI) may approach patients whom he feels may be suitable for entry into this study. The Principal Investigator (PI) should introduce the patient to the study by explaining the Protocol, procedures and objectives to the patient. The Principal Investigator (PI) will then provide an information sheet describing the study, potential discomforts, risks and benefits of participation. The patient will have sufficient time to decide whether they wish to participate in this study.

Any queries that patients may have regarding the study will be addressed appropriately by the Principal Investigator (PI), or another member of the study team at the center. Subjects will be instructed that they are free to obtain further information from the Principal Investigator (PI) at any time, that they are free to withdraw their consent and to discontinue their participation in the study at any time without prejudice.

If the patient is willing to participate in the study, he/she must read, understand and sign the informed consent form. The Principal Investigator (PI) will also sign this at the same occasion. Three copies of the consent form will be made. The original copy of the signed consent form will be kept in the Investigation Site File (ISF). A copy will be kept in the subject's medical notes and a further copy will be provided to the subject.

**Written informed consent from the subject must be obtained before any study related procedures are performed.**

Prior to evaluation of the study device, the following activities must be recorded as part of the subjects' records:

- Meeting all general inclusion/exclusion criteria
- Signing the Informed Consent Form
- Collecting demographic information

#### 7.1.2. Subject Eligibility

Once written informed consent has been obtained, the Case Report Form (eCRF) will be completed to document adherence to the inclusion and exclusion criteria.

Where a patient fails to fulfil any element of the inclusion and exclusion criteria, this will be documented and the signed consent form and completed inclusion/exclusion criteria retained by the Principal Investigator. The patient will not be advanced any further into this study.

### **7.1.3. Subject Identification**

When a subject is considered eligible for entry into this study, the subject will be allocated the next available investigation number (subject ID number), as assigned within the EDC (Electronic Data Capture) system, in order in which the subjects are entered.

For subjects enrolled, this number will consist of 01 for the first subject, 02 for the second subject and so on. This number will be the unique identifier of the subject and written on each page of the Case Report Forms (CRF) in the EDC system and all other documentation relating to that subject.

Once identified and approached a patient will be asked for consent as per section 7.1.1.

## **7.2. Pre-Treatment Evaluations**

### **VISIT 1:**

- Patient eligibility screening (Registration). Informed consent to be sought.
- Patient Initial exam
- Inter-occlusal space confirmation (static and dynamic) of clearance both for opposing edentulous area and rest area
- Initial impressions of opposing arch (alginate), and treatment arch with and without the existing Removable Partial Denture (RPD) in place
- Initial alginate impressions poured in diestone

### **Lab Stage 1, Post-Clinical Exam:**

- Survey & design, confirm contours are adequate for material
- Inter-occlusal space confirmation (static and dynamic) for clearance of both the opposing edentulous area and rest/clasp assembly area
- Custom tray fabrication (2mm spacer thickness) with extensions to adequately capture the edentulous areas

The first visit includes a standard oral examination. During this visit, impressions will be taken of the subject's mouth.

## **7.3. Treatment Evaluations**

### **VISIT 2: Patient Identification number assigned.**

Dentist and/or dental technician performs / records the following:

- Plaque scores
- An individual custom impression tray will be constructed by the clinician for each patient (to design of the Principal Investigator at each research site)
- Polyvinylsiloxane impressions will be completed
- Polyvinylsiloxane (PVS) impression poured in Diestone
- Framework hygiene disclose (of original appliance (Photograph)
- Bleeding on Probing (BOP) of abutment and adjacent teeth (limited perio exam; 6 point assessment)
- Pocket depths
- Mobility of the abutment teeth
- Health of Mucosal Bearing area
- Classification of occlusion: static and function
- Aesthetics (operator assessed)
- Photographs with and without appliance frontal, RL lateral & occlusal

**Patient assessments:**

- Assessment of satisfaction of current Removable Partial Denture (RPD) prostheses including: aesthetics, function, speech, eating, general comfort and complaints
  - clinician to confirm assessment
- Oral Health Impact Profile (OHIP) questionnaire completion

**LAB Stage 2:**

- Design on initial alginate cast (working cast not to be modified): teleconference confirmation / discussion between milling center, Dental technician, treating Dentist and Sponsor representative. To include clasp assembly design, location, bulk, undercuts, as well as major connector and other Removable Partial Denture (RPD) aspects
  - If consensus is not reached, treating Dentist will make final determination.
- Transfer of cast to milling center
- Milling Center scan
- Mill RPD
- Add occlusal wax rim on the Removable Partial Denture (RPD) frame edentulous area to accurately demonstrate tooth position and allow occlusal registration. Wax must be out of occlusion by 2mm space
- Verification of framework returned to treating Dentist

At the patients second visit a working impression will be constructed using the custom impression tray and an elastomeric impression material (polyvinyl siloxane or polyether).

**VISIT 3**

*Solvay Dental 360™**Strictly Confidential*

Dentist and/or dental technician performs / records the following:

- Tooth shade and mould selection
- Photographic verification of Removable Partial Denture (RPD) polymer frame fit: frontal, RL lateral, & occlusal
  - Only minimal adjustments permitted. If adjusted - record via photograph after adjustment
- Assess framework only on cast and in mouth for adaption and adequacy. Confirmation of occlusion with the polymer frame in place
- Confirm wax rim clinically including confirmation that there is 2mm of occlusion before proceeding with occlusal registration
- Jaw registration utilizing Polyvinylsiloxane (PVS) registration material. Confirmation by clinician that there is no occlusal contact or deformation of the polymer frame during this procedure
- Balance occlusion to be established if opposing a denture
- Ensure occlusal consistent with presenting condition and shape

**LAB Stage 3:**

- Articulate the casts on an articulator as indicated by the clinical center.
- Lab completes tooth set up in ideal occlusion, ensuring occlusion is consistent with the patient's presenting condition and CoCr RPD. Balanced occlusion to be established if opposing denture
- Photographs on cast

**VISIT 4**

- Patient wax tooth set-up and frame try-in
  - Clinician Assessment: evaluate occlusion, aesthetics, adaptation

**LAB Stage 4**

- Dental technical processes to finish

**VISIT 5**

Dentist performs and records the following:

- Assess fit
- Health of Mucosal Bearing area
- Mobility of the abutment teeth
- Classification of occlusal: static and function
- Aesthetics (operator assessed)
- Photograph of prosthesis in situ, ensuring fit of appliance
- Photographs with and without appliance frontal, RL lateral & occlusal
- Dentist delivers the Polymer Removable Partial Denture (RPD)

Patient assesses their current Cobalt Chrome dentures for the following, via the 5 point Likert scale:

- Comfort
- Aesthetics
- Chewing ability

The patient's original CoCr RPD will be taken and securely stored at the dentist's office for the 8 week test period. It may be tried in at the 1 week, 4 week and 8 week recall appointments to ensure they are still fitting and to assess any changes in tooth position and adaptation.

### **VISIT 6: Recall 1 week**

- Patient assessment of satisfaction of polymer appliance aesthetics, function, speech, eating, general comfort and complaint wearer – self reported and clinician confirmation

Dentist performs and records the following:

- Health of Mucosal Bearing area
- Abutment tooth mobility
- Classification of occlusal: static and function
- Aesthetics (operator assessed)
- Photographs with and without appliance frontal, RL lateral & occlusal
- Evaluation and photographic documentation of the Polymer Removable Partial Denture (RPD) for cracks, fractures, permanent deformation or other signs of mechanical failure
- Try-in of original CoCr RPD to assess fit and any changes in tooth position and adaptation

### **VISIT 7: Recall 4 week**

- Patient assessment of satisfaction of polymer appliance aesthetics, function, speech, eating, general comfort and complaint wearer – self reported and clinician confirmation

Dentist performs and records the following:

- Health of Mucosal Bearing area
- Abutment tooth mobility
- Classification of occlusal: static and function
- Aesthetics (operator assessed)
- Photographs with and without appliance frontal, RL lateral & occlusal
- Evaluation and photographic documentation of the Polymer Removable Partial Denture (RPD) for cracks, fractures, permanent deformation or other signs of mechanical failure
- Try-in of original CoCr RPD to assess fit and any changes in tooth position and adaptation

**VISIT 8: Recall 8 week**

Patient assesses the polymer denture for the following, via the 5 point Likert scale:

- Comfort
- Aesthetics
- Chewing ability
- Oral Health Impact Profile (OHIP) questionnaire completion

Dentist performs and records the following:

- Plaque scores
- Framework hygiene disclose
- Bleeding on Probing (BOP)
- Pocket depths
- Abutment tooth mobility
- Health of Mucosal Bearing area
- Classification of occlusal: static and function
- Aesthetics (operator assessed)
- Evaluation and photographic documentation of the Polymer Removable Partial Denture (RPD) for cracks, fractures, permanent deformation or other signs of mechanical failure
- Photographs with and w/o appliance frontal, RL lateral, occlusal
- Try-in of original CoCr RPD to assess fit and any changes in tooth position and adaptation
- Patient's original CoCr RPD is returned to the patient

**8. Adverse Events and Device Observations****8.1. Adverse Event (AE)**

An adverse event (AE) is defined according to the European Standard EN ISO 14155: as 'any untoward medical occurrence in a subject. An adverse event related to a device is defined as an 'adverse device effect' (ADE) and is defined as 'any untoward and unintended response to an investigational medical device'.

An adverse event or an adverse device effect may be mild, moderate or severe and are usually unexpected.

A device deficiency is defined as the inadequacy of a medical device with respect to its identity, quality, durability, reliability, safety or performance, which may include device malfunctions, user errors and inadequate labelling.

All adverse events, adverse device effects and or device deficiencies either observed by the Principal Investigator or reported by the subject, must be reported to the Sponsor within 24 hours.

To report an adverse event or adverse device effect or device deficiency, the Principal Investigator will complete an adverse event report form or relevant form located in the Case Report Form. The report will include the following information: device name, model number, lot/serial number, manufacturers date, expiry date, nature of event, severity, date of onset, duration, course and history of the adverse event/adverse device effect and causality. The subject will be questioned about any adverse event(s) and adverse device effect(s) at each visit.

### **8.1.1. Expected adverse events are as follows**

There are no expected Adverse Events for this study.

## **8.2. Reporting of Serious Adverse Events (SAE)/Serious Adverse Device Effects (SADE), Unanticipated Adverse Device Defects (UADE) and Device Deficiencies**

A serious adverse event is defined an adverse event that:

- led to death
- led to a serious deterioration in the health of the subject that either resulted in: a life-threatening illness or injury, or a permanent impairment of a body structure or a body function, or in-patient hospitalization or prolongation of existing hospitalization, or in medical or surgical intervention to prevent life-threatening illness or injury or permanent impairment to a body structure or a body function
- led to foetal distress, foetal death or a congenital abnormality or birth defect

Hospitalization is defined as greater than 24 hours in hospital.

A serious adverse device effect is defined as an adverse device effect that has resulted in any of the consequences characteristic of a serious adverse event or that might have led to any of these consequences if suitable action had not been taken or intervention had not been made or if circumstances had been less opportune.

An unanticipated serious adverse device effect (USADE) is defined as a serious adverse device effect which by its nature, incidence, severity or outcome has not been identified in the current version of the risk analysis report.

All serious adverse events, serious adverse device effects and/or device deficiencies that may have led to a USADE must be reported to the Sponsor or Sponsor Representative by telephone within 24 hours of the Principal Investigator becoming aware of it.

The Sponsor Representative can be contacted at the following numbers:

Contact Name: [name]

[contact]

Email: [contact]

The Principal Investigator should institute appropriate therapeutic and follow-up measures in accordance with good medical practice but should notify the monitor of such actions and record them in the subject's electronic Case Report Form. Each telephone reported reaction must be reported in writing to *Solvay Dental 360™* within 2 working days of the event.

It is also the responsibility of the Principal Investigator to inform the representative of the Institutional Review Board (IRB) in a timely manner.

### **8.3. Follow-up of Unresolved Events**

All serious adverse events, serious adverse device effects and/or unexpected adverse device effects will be followed until they are resolved or for 30 days after the subject's participation in the study ends.

#### **8.3.1. Anticipated clinical benefits**

The public will benefit from the study results which will help to refine the use of arylketone polymer (AKP) removable partial dentures (RPDs). This will help aid clinicians in the selection of materials to optimize their clinical outcomes of treatment.

#### **8.3.2. Risks associated with participation in the study**

Tooth movement may occur from the 1 week to 8 week recall visit that may result in the patient's original CoCr RPD not fitting as it used to. If this occurs a new metal RPD may have to be fabricated for the patient after the study has been completed.

There are no additional risks to the patient for participating in the study which he/she would not otherwise encounter with standard removable partial denture (RPD) assessments and fitting

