## 2.2. Risk/Benefit Analysis

Arylketone polymers provide an alternative to metal and acrylic denture frames that have previously been used in various medical device applications and have completed full biocompatibility testing.

There are no additional risks to the patient for participating in the study that he/she would not otherwise encounter with standard denture frame assessment and fitting. Standard procedures for

a removable partial denture includes an oral exam, impressions of the jaws, wax bite block, trial insertion of the framework and teeth, fitting and placement of the denture frame, followed by a final review visit.

The public will benefit from the study results that will help to refine the use of polymer removable partial dentures. This will help aid clinicians in the selection of materials to optimise their clinical outcomes of treatment. Data acquisition includes non-invasive collection methods before and after the fitting of the polymer denture frame. The goal of this study is to obtain data on patient centered outcomes on the Oral Health Related Quality of Life (OHRQoL) in patients wearing arylketone polymer (AKP) Removable Partial Dentures (RPDs). The results of this study will advance the design, fabrication and fitting of the polymer Removable Partial Denture (RPD) to further benefit the partially edentulous population. This will help aid clinicians in the selection of materials to optimise their clinical outcomes of treatment.

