12.9 Safety Analysis

There are no expected adverse events for this study. However, any adverse events reported will be listed and summarized.

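### Tooth movement is named as a risk of taking part, but the risk statements disagree on it and the SAP never summarises the CoCr try-in that would show it

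*Protocol*

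**What the plan says.** **The risk.** Protocol 8.3.2 states: "Tooth movement may occur from the 1 week to 8 week recall visit". It says the original CoCr denture may then not fit as it did, and adds: "If this occurs a new metal RPD may have to be fabricated for the patient after the study has been completed". The next paragraph of the same section says: "There are no additional risks to the patient for participating in the study which he/she would not otherwise encounter" in standard denture care.

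**Statements elsewhere.** Protocol 2.2 says: "There are no additional risks to the patient for participating in the study that he/she would not otherwise encounter with standard denture frame assessment". It does not mention tooth movement. Protocol 8.1.1 says: "There are no expected Adverse Events for this study". SAP 12.9 says: "There are no expected adverse events for this study", then that whatever is reported as an adverse event will be listed and tabulated.

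**The measurement.** Under Protocol 7.3, the CoCr denture is kept at the dental office from Visit 5. Visit 6 lists, among the items the dentist carries out and records: "Try-in of original CoCr RPD to assess fit and any changes in tooth position and adaptation". Visits 7 and 8 list the same item. The Visit 5 text is permissive: it allows a try-in at the three recall visits but does not require one.

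**The analysis.** The SAP does not mention the try-in, the fit of the CoCr denture after baseline, tooth position, or replacement metal dentures.

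**The concern.** Subjects enter the study routinely wearing a CoCr denture (Protocol 6.1). The study keeps it for eight weeks, and the protocol accepts that it may not fit as before when it is returned. That is a foreseeable cost of taking part, and the protocol schedules three checks for it.

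Two gaps could keep the result out of the report. First, the documents do not say whether tooth movement or a failed try-in is an adverse event, so sites may classify the same finding differently. Classification has consequences: the follow-up rule in Protocol 8.3 covers serious events and unexpected device effects, and tooth movement is unlisted in 8.1.1 but foreseen in 8.3.2. Second, if a finding is not reported as an adverse event, no SAP table picks it up. At stake is the completeness of the safety results, not the primary comparison.

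**Working it through.** The plan states no rate of tooth movement, so there is no figure to reproduce. The check is a comparison of texts, followed by a short calculation of what the missing table could show.

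**Step 1: do the risk statements agree?**

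- Protocol 8.3.2 against Protocol 2.2: they disagree. One names a risk of taking part; the other says there is none beyond standard care and makes no exception.
- Protocol 8.3.2 against Protocol 8.1.1 and SAP 12.9: unresolved. A possible event need not be an expected one, and 8.3.2 does not call tooth movement an adverse event. But the definition in Protocol 8.1 is broad enough to include movement that spoils the fit of a denture, and nothing says whether it does.
- Protocol 8.3.2 against itself: no firm conflict. Its second paragraph can be read as saying there is nothing further besides tooth movement.

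**Step 2: is the try-in always done?** Visits 6, 7 and 8 list it as performed and recorded. Visit 5 makes it optional. The number of subjects with a result at each visit is therefore uncertain.

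**Step 3: does any SAP section report it?**

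- 11.3 (visit list): try-in not mentioned.
- 12.6.3: health of the mucosal bearing area only.
- 12.6.4: abutment tooth mobility at Visits 2 and 8. Mobility is related, but it is neither tooth position nor fit of the CoCr denture.
- 12.6.5: the objective includes fit, but only operator-rated aesthetics is reported.
- 12.6.1, 12.6.2, 12.6.6 and 12.6.7: plaque and bleeding, patient ratings, preference.
- 12.7: no further analyses planned.
- 12.9: only what has been reported as an adverse event.
- 12.10: protocol deviations.

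Three try-ins are scheduled, and no SAP section analyses them.

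**Step 4: what could a table show?** Inputs from Protocol 12.2 and SAP 10: 40 enrolled and 10% attrition, so 40 × (1 − 0.10) = 36. The event counts below are illustrative assumptions.

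Exact (Clopper-Pearson) two-sided 95% limits for x events in n try-ins are the 0.025 quantile of Beta(x, n − x + 1) and the 0.975 quantile of Beta(x + 1, n − x). With x = 0 the upper limit is 1 − 0.025^(1/n).

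- 0/40: 1 − 0.025^(1/40) = 8.8%. 0/36: 1 − 0.025^(1/36) = 9.7%.
- 2/40 = 5.0% (0.6% to 16.9%). 2/36 = 5.6% (0.7% to 18.7%).
- 4/40 = 10.0% (2.8% to 23.7%). 4/36 = 11.1% (3.1% to 26.1%).

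The chance of at least one case is 1 − (1 − p)^n. For assumed true rates p of 2%, 5% and 10%, it is 55%, 87% and 99% with n = 40, and 52%, 84% and 98% with n = 36. A study of this size would probably see a case if the rate were a few percent, but it could not rule out such a rate by seeing none.

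**The case against.** The strongest reply is that the safety system already covers this. Protocol 8.1 requires every adverse event, device effect and device deficiency to reach the sponsor within 24 hours, has subjects asked about events at each visit, and says such events are usually unexpected. SAP 12.9 then lists and tabulates them. SAP 12.3 summarises discontinuations with reasons, and 12.6.4 reports abutment mobility. All of this stands, and it rules out two stronger readings:

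- A reader might infer that Protocol 8.1.1 discourages reporting of tooth movement. The documents do not support that; being unlisted is no reason to withhold a report.
- A reader might infer that the report will be silent on this harm. It will not be if sites report it as an adverse event. What is missing is a rule that makes them do so consistently, or a table that does not depend on it.

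A reader might also infer that patient preference, collected at Visit 8 together with the last try-in, is biased towards the polymer denture because the CoCr one no longer fits. That is speculative. The order of events within Visit 8 is not stated, no evidence on the direction or size of any shift is given, and movement while wearing the polymer denture could itself be an effect of that frame. Splitting preference by CoCr fit would condition on a post-baseline outcome, with perhaps a handful of subjects in one group, in a SAP that plans no subsets (12.8). No such split is proposed.

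Finally, the confidence limits are general binomial arithmetic and do not themselves show a defect. That is correct; they show only what the table could say.

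**Conclusion.** The point holds in limited form. Protocol 2.2 and 8.3.2 disagree. Protocol 8.1.1 and SAP 12.9 leave the classification of tooth movement open. A scheduled assessment of the one specific participation harm that the protocol names has no place in the analysis plan, so that harm may be missing from the safety results. The primary endpoint, hypothesis test and sample size are not affected.

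The size of the harm is unknown because the documents give no rate. With no cases seen, the data would be compatible with rates up to 8.8% (40 try-ins) or 9.7% (36), so a bare statement that none occurred would need its interval.

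It would go too far to call tooth movement the only harm that taking part can cause, or to say that subjects lose a working denture. It is the only specific harm named, and the text says that the denture may not fit as it did. The case report forms and consent pages are not among the documents, so which try-in fields are collected and what patients were told cannot be judged.

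**What to change.** 1. Reconcile Protocol 2.2, 8.1.1 and 8.3.2 and SAP 12.9 so that they make one statement about tooth movement, including how it and a failed try-in are classed for reporting. Which class applies is for the sponsor and investigators to decide.
2. Reconcile the Visit 5 text with the Visit 6, 7 and 8 lists on whether the try-in is always done.
3. Add to SAP 12.9 a descriptive table for Visits 6, 7 and 8: the number of subjects whose CoCr denture no longer fits as before, and the number with a change in tooth position, each as n/N with an exact 95% confidence interval. N is the number of completed try-ins at that visit.
4. List any known need for a new metal denture. A listing is enough, because replacement would come after the study and may not be fully captured.

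The cost is a wording change in each document and one extra table. The Visit 2 list in Protocol 7.3 has no explicit operator grade for the fit of the CoCr denture, so a simple fit field on the case report form may also be needed if none exists. No visit, sample-size change or test is added.
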